Endothelial cell perturbation and reduced pulmonary blood flow may be relevant to the pathogenesis of emphysema^{31,32} and important in AATD. AAT has been shown to attenuate endothelial apoptosis in animal models of emphysema.^{33,34} We examined the endothelial hypothesis of emphysema in the MESA COPD Study (AAAD6395), a case-control study of COPD, in which we found pulmonary microvascular blood flow on contrast-enhanced magnetic resonance imaging (MRI) to be inversely associated with CT percent emphysema and COPD stage, and associated with CD31 $^{+}$ endothelial microparticles (EMPs), which reflect endothelial apoptosis.^{35,37} In the Alpha-1 Foundation-funded study “Pulmonary Vascular Damage in Alpha-1 Antitrypsin Deficiency”, which followed the MESA COPD protocol, we found greater CD31 $^{+}$ EMPs in AATD compared to MESA COPD cases and controls, and a non-significant reduction in pulmonary microvascular blood flow in AATD compared to controls. Importantly, those with

AATD on AAT augmentation had lower CD31⁺ EMPs and a trend toward greater pulmonary microvascular blood flow compared to those not on AAT therapy. These findings demonstrate increased endothelial damage in AATD compared to non-AATD COPD and suggest amelioration of endothelial damage by AAT augmentation; however whether AAT augmentation reduces CD31⁺ EMPs and improves pulmonary microvascular blood flow is unknown.

Therefore, we propose to accrue 15 subjects with PiZZ AATD-associated lung disease who are on AAT augmentation therapy into a study protocol that includes: 1) a Phase IIa cross-over randomized controlled trial (RCT) of aspirin vs. placebo and 2) a withdrawal study with a follow-up visit off AAT augmentation therapy in order to test the following hypotheses:

- 1) Randomization to aspirin 81mg daily increases pulmonary microvascular blood flow on MRI and improves secondary endpoints compared to placebo in participants with AATD-associated lung disease receiving standard care (including AAT augmentation therapy).
- 2) CD31⁺ EMPs will be lower and secondary endpoints will be improved when participants are on AAT augmentation therapy compared to off AAT augmentation therapy, while receiving other standard medical treatment.

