Successful completion of these aims would demonstrate that aspirin and AAT augmentation therapy improve pulmonary microvascular blood flow and reduce CD31⁺ EMPs in AATD-related lung disease, would support future studies evaluating aspirin in emphysema in AAT, demonstrate additional benefits of AAT augmentation, and support the use of pulmonary MRI and EMPs as outcomes for clinical trials in COPD.

2. Study Design

- a. The proposed study is a single-center Phase IIa randomized cross-over study and withdrawal study.
- b. The study will accrue 15 subjects and enroll up to 20.
- c. Inclusion criteria:
 - i. Alpha-1 antitrypsin deficiency (PiZZ genotype)
 - ii. 40 years of age or older
 - iii. Evidence of emphysema on CT scan as read by a Radiologist
 - iv. On intravenous alpha-1 antitrypsin replacement therapy
- d. Exclusion criteria:
 - i. Platelet count < 150,000/dL, history of intracranial hemorrhage or severe GI bleed, use of systemic anticoagulant, physician prescribed use of antiplatelet drug (including aspirin and P2Y12 receptor inhibitors), or known severe liver disease;
 - ii. Immunosuppression by use of medications (including oral prednisone) or medical condition (organ transplantation or actively-treated malignancy), including autoimmune conditions that require immunomodulatory treatment (e.g. anti-TNF agents);
 - iii. Known atrial fibrillation or left ventricular (LV) systolic heart failure;
 - iv. Contraindication to MRI, including pregnancy, weight > 300 lbs (due to weight limits of the machine), those with pacemakers, aneurysm clips, cochlear implants or other implanted electronic devices, or severe claustrophobia;

- v. Chronic renal insufficiency (estimated GFR < 45 L/min/1.73 m² or self report) due to slightly increased risk of nephrogenic systemic fibrosis from gadolinium administration and aspirin-related renal insufficiency. GFR will be calculated using the MDRD equation based on the most recent laboratory sample available (within the last 30 days required). If one is not available at the time of MRI a point-of-care Creatinine will be run and this value will be used instead of the laboratory sample;
- vi. Frequent exacerbations of respiratory symptoms (two or more in the last year); and
- vii. Exacerbation of respiratory symptoms within the previous 6 weeks, such as that requiring hospitalization, oral prednisone or antibiotics to control symptoms.

[figure not shown]

Figure 1. Study Design

Table 1: Study Components

Visit #:	1	2	3	4

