Exam component	Screening visit	After treatment 1	After treatment 2	Off AAT augmentation
Anthropometry	X	X	X	X
Blood pressure		X	X	X
Questionnaires	X	X	X	X
Phlebotomy				
Endothelial microparticles		X	X	X
Creatinine, CBC	X	X	X	X
Platelet activation		X	X	X
Alpha-1 antitrypsin level		X	X	X
Urine specimen		X	X	X
Spirometry, pre- and post-bronchodilator	X	X	X	X
Diffusing capacity	X	X	X	X
Pulse oximetry	X	X	X	X
Six minute walk test		X	X	X
Non-contrast chest CT	X			
Cardiopulmonary MRI				
Pulmonary microvascular blood flow		X	X	X
RV, LV, cardiac output		X	X	X

- e. Endpoints
 - i. Aspirin RCT
 - (1) Primary endpoint: pulmonary microvascular blood flow
 - (2) Secondary endpoints:
 - a. Pulmonary perfusion: pulmonary microvascular blood volume, pulmonary microvascular transit time, and above measures of pulmonary perfusion in areas of emphysema on chest CT
 - b. CD31+ endothelial microparticles (reflecting endothelial apoptosis), CD62+ endothelial microparticles (reflecting endothelial activation)
 - c. Spirometry: post-bronchodilator FEV₁ and FEV₁/FVC
 - d. Pulse oximetry
 - e. Diffusing capacity
 - f. Six minute walk test
 - g. Alpha-1 antitrypsin level
 - h. Cardiac MRI: LV EDV, RV EDV, LV SV, cardiac output
 - i. Questionnaire: MMRC dyspnea scale, COPD Assessment Test
 - ii. Alpha1 Augmentation Withdrawal Study
 - (1) Primary endpoint: CD31+ endothelial microparticles (reflecting endothelial apoptosis)
 - (2) Secondary endpoints:
 - a. CD62+ endothelial microparticles (reflecting endothelial activation), platelet microparticles (reflecting platelet activation)
 - b. Pulmonary perfusion: pulmonary microvascular blood flow, pulmonary microvascular blood volume, pulmonary microvascular transit time, and above measures of pulmonary perfusion in areas of emphysema on chest CT
 - c. Spirometry: post-bronchodilator FEV₁ and FEV₁/FVC
 - d. Pulse oximetry
 - e. Diffusing capacity
 - f. Six minute walk test
 - g. Markers of platelet activation: beta-thromboglobulin, platelet factor 4, thromboxane B2, von Willebrand factor
 - h. Cardiac MRI: LV EDV, RV EDV, LV SV, cardiac output
 - i. Questionnaire: MMRC dyspnea scale, COPD Assessment Test

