 - f. Subjects will undergo telephone pre-screening before Visit 1. At Visit 1 they will be consented, after which a platelet count and creatinine will be drawn to confirm eligibility. Participants will then complete questionnaires, perform spirometry, diffusing capacity and pulse oximetry. Eligible patients will then be randomized as to the order of intervention vs. placebo and will undergo non-contrast chest CT. Randomization will be stratified by smoking status with full concealment of allocation; subjects and the investigative team will be blinded as to treatment assignment. The intervention will be 81mg aspirin and a matched placebo, each taken once per day in the morning. Each treatment will last approximately 2 weeks (Figure 1, previous page) with Visits 2 and 3 occurring at the end of treatment 1 and 2, respectively. Each treatment may be continued for up to 18 days, if needed, to coordinate scheduling of the participant visit and procedures. There will be a 2-week washout period between the treatments, and the total length of the randomized protocol will be approximately 6 weeks. The CU Research

Pharmacy will dispense study medications. During the study period, subjects will be asked to continue the same medication regimen and avoid using over-the-counter aspirin and other non-steroidal anti-inflammatory drugs.

- g. Timing with respect to AAT infusions: We will recruit subjects who are on AAT augmentation therapy, and the timing of study visits will be coordinated with their weekly dosing of AAT to minimize differences between study visits other than the intervention. We will schedule patient visits on days 1-3 post-infusion in order to study the effects of peak AAT levels.
- h. Withdrawal of AAT augmentation therapy:
Subjects will be asked to stop AAT augmentation therapy for approximately 5 weeks and return for Visit 4. Withdrawal of AAT for 5 weeks (a maximum of 5.5 weeks) will allow AAT levels to drop briefly to those seen in the absence of AAT augmentation.

3. Statistical Procedures

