- a. Data analysis: Data analysis will be performed primarily by the PI at Columbia University. The primary analysis will use paired t-tests to compare pulmonary microvascular blood flow on aspirin compared to placebo, and CD31⁺ EMPs on AAT augmentation therapy compared to off augmentation following the intention-to-treat principle. Similar analyses will be performed for secondary endpoints. Exploratory analyses will also evaluate for different effects in subgroups by smoking status, COPD severity, use of supplemental oxygen, and by severity of reduction in DLCO and will evaluate for period and carryover effects. Approaches to missing data will include: 1) minimization through short study duration and efforts to retain 100% of participants for 3 months and 2) sensitivity analyses using a variety of imputed values (worst-case scenario, baseline observation carried forward, last observation carried forward).
- b. Statistical power: Power was estimated for a paired t-test to compare an individual's pulmonary microvascular blood flow before and after the intervention. For 15 subjects with power of 80% and $\alpha=0.05$, we will be able to detect a minimally significant difference of 0.30 log CD31⁺ EMPs (1.2 SDs of the difference in log CD31⁺ EMPs for those on replacement and not), and a minimally significant difference of 48.4 mL blood/min*100mL lung (1.6 times the SD of the difference in pulmonary microvascular blood flow [PMBF] for those on replacement and not). Power will be adequate for CD31⁺ EMPs and moderate for PMBF. As power was derived from a cross-sectional analysis, this is a conservative estimate and we expect that power will be improved when comparing changes within an individual.

4. Recruitment and Consent

- a. Recruitment: Participants will be recruited from multiple sources. First, we will recruit among the 30 participants who previously enrolled in the Alpha-1 extension of the MESA COPD Study over the telephone (AAAD6395). All of these participants agreed to be contacted for future research purposes on their consent forms. Second, we will email,

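### Must section 3.a name which on-augmentation visit is paired with Visit 4 in the AAT withdrawal analysis?

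*Combined protocol and SAP*

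**What the plan says.** Section 3.a makes the withdrawal primary analysis a paired t-test of CD31+ "EMPs on AAT augmentation therapy compared to off augmentation following the intention-to-treat principle", and extends similar analyses to the secondary endpoints.

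The visit structure comes from sections 2.f to 2.h, Table 1 and section 5 (item 4):

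- Treatment order is random: "Eligible patients will then be randomized as to the order of intervention vs. placebo".
- Both treatment visits fall while augmentation continues, with "Visits 2 and 3 occurring at the end of treatment 1 and 2, respectively". Between the periods, "There will be a 2-week washout period between the treatments".
- Augmentation is then stopped for about 5 weeks before Visit 4.
- EMPs are measured at Visits 2, 3 and 4, not at Visit 1.

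Hypothesis 2 in section 1 describes the contrast as on augmentation "compared to off AAT augmentation therapy, while receiving other standard medical treatment". Section 2.g times visits around the infusions so that they differ as little as possible apart from the intervention. The exclusion criteria in 2.d rule out "physician prescribed use of antiplatelet drug (including aspirin and P2Y12 receptor inhibitors"), and 2.f asks participants to avoid over-the-counter aspirin during the study.

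**The concern.** A paired test needs one on-augmentation value per participant, and this design produces two. Three pairings with Visit 4 can be read into the text: the placebo-period visit, the mean of Visits 2 and 3, or Visit 3 as the last visit before withdrawal.

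They do not estimate the same quantity if aspirin affects the endpoint, and the trial's own hypothesis allows for that. Section 2.e lists "CD31+ endothelial microparticles (reflecting endothelial apoptosis), CD62+ endothelial microparticles" among the aspirin secondary endpoints, and hypothesis 1 states: "Randomization to aspirin 81mg daily increases pulmonary microvascular blood flow on MRI and improves secondary endpoints compared to placebo". If aspirin lowers CD31+ EMPs, any pairing that includes the aspirin visit lowers the on-augmentation value and flatters augmentation.

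The same question arises for the other withdrawal endpoints first measured at Visit 2: CD62+ EMPs, platelet microparticles and activation markers, MRI perfusion, cardiac MRI and the six minute walk. An open definition could also be settled after unblinding.

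**Working it through.** **The plan's own figure.** Section 3.b gives a detectable difference of 0.30 log CD31+ EMPs, equal to 1.2 SDs, for 15 subjects, 80% power and alpha 0.05. The implied SD of the difference is 0.30 / 1.2 = 0.25 log. A two-sided paired t-test with n = 15 detects 0.778 SD at 80% power, which is 0.778 × 0.25 = 0.19 log, so the stated 0.30 is not reproduced. Section 3.b says its inputs are cross-sectional and conservative. That mismatch is separate from the present point, but it means the SD is uncertain. I therefore also use the SD at which 0.30 log would be the detectable difference: 0.30 / 0.778 = 0.386 log.

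**Share of an aspirin effect A that enters the augmentation contrast**, with no carryover:

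- Placebo-period visit: 0.
- Visit 2/3 mean: A / 2.
- Visit 3: A × k / 15, where k participants take aspirin second. With k = 7 or 8 this is 0.47A to 0.53A. The allocation ratio is not stated, so balance is an assumption.

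**False-positive rate with no augmentation effect**, n = 15, two-sided 0.05. A is assumed, because no document gives it. The rate for the mean comes from the non-central t with non-centrality (A / 2) × √15 / SD. The SD for the mean is either the single-visit value or that value × √0.75 (independent, equal visit errors). Visit 3 is simulated with k = 7 or 8.

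| Pairing with Visit 4 | SD 0.25, A = 0.05 | SD 0.25, A = 0.10 | SD 0.386, A = 0.05 | SD 0.386, A = 0.10 |
|---|---|---|---|---|
| Placebo-period visit | 5% | 5% | 5% | 5% |
| Visit 2/3 mean | 6.5–7.0% | 11.2–13.3% | 5.6–5.8% | 7.5–8.4% |
| Visit 3 | 6.2–6.6% | 9.7–11.3% | 5.5–5.7% | 7.0–7.6% |

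With order unbalanced at 11 of 15 on aspirin at Visit 3, that pairing reaches 17.8% at SD 0.25 and A = 0.10.

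**Carryover.** If a quarter to a half of A persisted into the placebo visit of aspirin-first participants (7 or 8 of 15), the placebo pairing gives 5.0% to 6.6%. The largest mean bias is 0.5 × 0.10 × 8/15 = 0.027 log. The mean is affected too: with half of A persisting in half the participants, it carries (1 + 0.5 × 0.5) / 2 = 0.625 of A. The placebo visit of aspirin-first participants falls about 4 weeks after their last study aspirin (2-week washout plus about 2 weeks of placebo).

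**Price of the placebo pairing.** At SD 0.25 its standard error is 0.25 / √15 = 0.065 log. For the mean it is 0.065 × √0.75 = 0.056 log, so the ratio is 1 / √0.75 = 1.155. Detectable differences are 0.19 against 0.17 log; at SD 0.386 they are 0.30 against 0.26 log.

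**Choosing afterwards.** With no aspirin or augmentation effect and independent, equal visit errors, keeping the best of the three pairings gives about 10% false positives.

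**What the text points to.** Hypothesis 2 holds other standard treatment constant. Study aspirin is the trial's experimental drug, and prescribed aspirin is an exclusion, so an aspirin-period visit fits that description poorly. Section 2.g is written about infusion timing, but its stated aim of keeping visits alike points the same way. Visit 4 has no study aspirin described, so its natural counterpart is the placebo-period visit. Under intention to treat, that visit follows from the randomised sequence, with no further discretion.

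**The case for a change.** The strongest argument for a change is that this is one of only two primary analyses, with 15 participants, and its comparator is nowhere stated in the readable text. Hypothesis 2 and section 2.g lean toward the placebo visit but do not say so. No pre-treatment EMP sample exists to settle the matter. On the sponsor's own hypothesis an aspirin effect is expected, and a sentence before unblinding would cost nothing.

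The textual observation stands: the definition is absent from what can be read. The rest is weaker. Figure 1 is not available here, and a design figure may well mark the on/off comparison, so its absence cannot count against the plan. The three readings are not equally open. The Visit 3 reading borrows before-and-after wording from a power sentence in 3.b about blood flow. The bias needs an aspirin effect of a size no document supplies, together with an analyst who pairs an aspirin-period value with Visit 4. The 10% figure needs someone to try several pairings and report the best, and nothing in the plan suggests that.

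Nor is the placebo pairing the only defensible one. Averaging Visits 2 and 3 is more precise, and a model of Visits 2 to 4 with an aspirin term would use all the data while separating the aspirin effect. No pairing removes the confounding of time with augmentation status, because the off-augmentation value is always Visit 4. The placebo pairing also makes the interval to Visit 4 depend on sequence: about 5 weeks for aspirin-first and about 9 weeks for placebo-first, if withdrawal starts straight after Visit 3.

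**Conclusion.** No change follows. This is missing detail that an analyst fills sensibly, not a stated rule that gives a wrong answer. The plan collects the aspirin-free on-augmentation value for every participant who completes the visits, and hypothesis 2 read with section 2.g leads to it. Used that way, the withdrawal test keeps its 5% level absent carryover, and stays at or below 6.6% if up to half of a 0.10 log aspirin effect persisted.

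Other pairings would do harm only if aspirin moves CD31+ EMPs materially. At an assumed 0.05 log with balanced order the rate is 5.5% to 7.0%, close to nominal. At 0.10 log it is 7.0% to 13.3%, and higher if order is unbalanced. Choosing between the placebo visit and a more precise use of both visits is a trade-off of about 15% in standard error, on which competent analysts may differ.

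The conclusion rests on the readable text, on n = 15 with SDs of 0.25 to 0.386 log, and on the absence of any sign that the pairing would be picked after seeing results.

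### Both hypotheses and the Section 1 success statement reach into the secondary endpoints, but Section 3.a tests 18 or 19 aspirin and 23 withdrawal secondaries with no order, adjustment or exploratory label

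*Combined protocol and SAP*

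**What the plan says.** Section 2.e names one primary endpoint per study. For the aspirin trial it reads "Primary endpoint: pulmonary microvascular blood flow", and CD31+ EMPs appear among the secondaries. The withdrawal study reverses this: CD31+ EMPs are primary and PMBF is secondary. Long secondary lists follow in both.

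Section 3.a begins "The primary analysis will use paired t-tests to compare pulmonary microvascular blood flow on aspirin compared to placebo", adds the matching test of CD31+ EMPs on and off augmentation, and continues "Similar analyses will be performed for secondary endpoints". Only the subgroup, period and carryover analyses are called exploratory. A significance level of 0.05 appears only in the power paragraph (3.b), and sidedness is not stated.

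Two places in Section 1 go beyond the primaries:

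- Hypothesis 1 is that aspirin "increases pulmonary microvascular blood flow on MRI and improves secondary endpoints compared to placebo". Hypothesis 2 has parallel wording for augmentation. Neither says which secondaries, or how many, must improve.
- The closing statement of the rationale reads "Successful completion of these aims would demonstrate that aspirin and AAT augmentation therapy improve pulmonary microvascular blood flow and reduce" CD31+ EMPs.

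**The concern.** The hypotheses treat the secondary endpoints as something the trial tests and may confirm, and the analysis section gives them the same test as the primaries. Because a different set of analyses is labelled exploratory, a reader will take the secondaries to be inferential.

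Nothing then limits what a nominally significant secondary result may support. If a study's primary endpoint fails, one p-value below 0.05 among 18 to 23 could still be offered as evidence that secondary endpoints improve. If it fell on CD31+ EMPs for aspirin, or on PMBF for augmentation, it could be offered as one of the effects that Section 1 says would be demonstrated. The first case is plausible in the aspirin trial, because 3.b itself rates power for PMBF as only moderate. Section 1 expects the results to inform later aspirin studies and the case for augmentation, so a chance finding could influence both.

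**Working it through.** **The plan's own figures.** The plan gives no endpoint count and no familywise error rate, so there is none to reproduce. Its only related figures are the detectable differences in 3.b (1.2 SD for CD31+ EMPs, 1.6 SD for PMBF; 15 subjects, 80% power, 0.05). A two-sided paired t-test with n = 15 detects 0.78 SD at 80% power, so they do not reproduce. That is a separate matter, and nothing below depends on it.

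**Step 1: count the secondaries in Section 2.e.**

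| Group | Aspirin | Withdrawal |
|---|---|---|
| Microparticles | 2 | 2 |
| Perfusion, whole lung | 2 | 3 |
| Perfusion in emphysema areas | 2 or 3 | 3 |
| Spirometry | 2 | 2 |
| Oximetry, diffusing capacity, six-minute walk | 3 | 3 |
| AAT level | 1 | – |
| Platelet markers | – | 4 |
| Cardiac MRI | 4 | 4 |
| Questionnaires | 2 | 2 |
| **Total** | **18 or 19** | **23** |

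The aspirin total is 19 if the emphysema-area measures include PMBF, and 18 if they repeat only the two secondary measures listed just before.

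**Step 2: chance of at least one nominally significant secondary result when no effect is real.** Two-sided 0.05 is assumed.

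- Independent, either direction: 1 − 0.95^19 = 62.3%; 1 − 0.95^23 = 69.3%. With 18 endpoints: 1 − 0.95^18 = 60.3%.
- Independent, favourable direction only (0.025 per test): 1 − 0.975^19 = 38.2%; 1 − 0.975^23 = 44.1%.
- Correlated: simulation of 100,000 sets of n = 15 paired t-tests with a common correlation between the endpoints' paired differences, each signed so that positive is favourable.

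| Assumed correlation | Aspirin (19), either / favourable | Withdrawal (23), either / favourable |
|---|---|---|
| 0 | 62.3% / 38.2% | 69.3% / 44.1% |
| 0.3 | 53.8% / 28.2% | 59.5% / 31.6% |
| 0.5 | 42.7% / 21.6% | 47.0% / 23.5% |
| 0.7 | 30.1% / 15.0% | 32.5% / 16.2% |
| 0.8 | 23.7% / 11.9% | 25.4% / 12.6% |

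The rows for correlation 0 are the exact values. A single favourable-direction test has a 2.5% chance.

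**Step 3: expected number of favourable false positives,** whatever the correlation: 0.025 × 19 = 0.475 for aspirin and 0.025 × 23 = 0.575 for withdrawal.

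**Step 4: the two effects per study in the Section 1 statement.** Each study has one primary and one secondary effect. Tested separately at 0.05, the chance of at least one false positive in a study is 1 − 0.95^2 = 9.75% if independent (about 9.1% by simulation at correlation 0.5). Testing the second only after the primary is significant holds it at 5%.

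**The case against.** The strongest reply is that this is a 15-subject, single-center Phase IIa study. Section 8 speaks of exploring intermediate endpoints, and unadjusted secondaries are common at this stage. The Section 1 statement is conditional rationale, not a decision rule. It follows hypotheses that pair aspirin with PMBF and augmentation with CD31+ EMPs, so it could be read respectively, as restating the two primaries.

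Much of this stands. It rules out several stronger readings:

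- A reader might infer that the plan has no hierarchy at all. It does: one primary per study is named in 2.e and again in 3.a. What is missing is a rule for everything below it.
- A reader might infer that the plan allows a secondary result to replace a failed primary. No sentence says so. The plan simply does not prevent it.
- A reader might count 0.05 × 42 = 2.1 expected false positives and conclude that one or two false claims of improvement are likely. That total covers both studies and both directions. The favourable count is about half of one per study.
- A reader might set 1 − 0.95^4 = 18.5%, for four effects, against 5% after a fix. The first pools both studies and includes both primaries; the second is per study. Like for like, the change is 9.75% to 5% per study, or 18.5% to 9.75% pooled.

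The independent figures are also an upper end: perfusion measures recur in emphysema areas and the cardiac measures come from the same scan. Some endpoints, such as ventricular volumes, have no stated favourable direction.

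The reply does not dispose of the hypotheses. They include improvement in the secondary endpoints however the Section 1 statement is read, and the secondaries are not labelled exploratory although other analyses are.

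**Conclusion.** The point holds as a mismatch between what the trial proposes to claim and what its analysis section can support. It does not touch the primary analyses, which keep one test each at 0.05.

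If no secondary effect is real, the chance of at least one favourable nominal result ranges from 38% (aspirin) and 44% (withdrawal) under independence to about 12% and 13% at a correlation of 0.8. At 0.5 it is about 22% and 24%. In either direction, the figures at independence are 62% and 69%, and at 0.5 about 43% and 47%. These rest on two-sided testing at 0.05, 19 aspirin endpoints, and common correlations that are assumptions, since the documents give none. If testing were one-sided at 0.05 in the favourable direction, the independent figures would be 62% and 69%.

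That two of the four effects in the Section 1 statement are secondary depends on its plain reading, because nothing in it says respectively. The problem with the two hypotheses does not depend on that reading. This should be changed, but it is not a flaw that invalidates the trial.

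**What to change.** In 3.a, state that secondary endpoints will be reported as mean paired differences with 95% confidence intervals, unadjusted and labelled exploratory, and that no claim of improvement will be drawn from a nominal p-value. State the significance level and sidedness for the two primary tests there as well.

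Reword the success statement and both hypotheses in Section 1 so that claims of demonstrated effect or improvement rest only on PMBF for aspirin and CD31+ EMPs for AAT withdrawal.

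If the sponsor wants to claim the second effect in either study, name it in 3.a and test it at 0.05 only if that study's primary is significant. This is optional. Its drawback is greatest in the aspirin trial, where CD31+ EMPs would sit behind a primary that the plan rates as only moderately powered.

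A Bonferroni correction over all secondaries is not recommended. At 0.05/42 = 0.0012 per test, the effect detectable with 15 pairs at 80% power rises from 0.78 to 1.30 SD.

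The cost is a few sentences, with no extra patients or data, and the primary tests keep their full alpha. The price is that secondary findings cannot be presented as demonstrated, and a sequenced second claim is lost if the primary fails.

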7. Diffusing capacity. This non-invasive test is similar to spirometry, but involves less effort. All participants will undergo single breath DLCO at visits 1-4.
8. Pulse oximetry, or oxygen saturation. Resting oxygen saturation (off supplemental oxygen for 5 minutes, if used) will be measured non-invasively with a pulse-oximeter at visits 1-4.
9. Six minute walk test. The 6MWT will be conducted on an established course according to ATS standards by a certified and trained technician with continuous non-invasive monitoring (e.g. oxygen saturation).
10. CT scan. The CT scan will be performed using a GE 64 multi-detector computed tomography (MDCT) scanner at visit 1. The protocol comprises a full scan of the chest following instructions for a very deep breath. The purpose of this test is to measure the full lung and lung segments and regions, and the total pulmonary vasculature volume. At the end of the study, participants will be asked to breathe out and hold it for a few seconds to be able to take an expiratory phase scan. The estimated effective radiation exposure for the inspiratory and expiratory scans is 6.5 mSv total. Women age 40-55 years will have a urine pregnancy test performed prior to CT and MRI scanning.
11. Magnetic Resonance Scanning on MRI scanners. The MRI exam will be performed at visits 2-4. Before having the MRI exam, participants will be asked questions about their medical history and any contraindications to MRI. The MRI will be a pulmonary angiography with the administration of gadolinium to visualize the pulmonary vascular bed. For this exam, the participant will lie on a table inside the MRI for about 30 minutes and will wear a facemask delivering supplemental oxygen at 8 L/min to reverse pulmonary hypoxic vasoconstriction. Gadolinium contrast will be injected into the antecubital vein through an 18-20 gauge IV. The type of gadolinium will be gadoterate meglumine (a macrocyclic agent, Dotarem), and the dose per scan will be 0.03 mmol/kg (0.06 ml/kg). The scanning will be at Functional Residual Capacity (FRC), which is the volume of air left in the lungs after a normal, passive exhalation. Participants will be asked to breathe out to a resting phase, and will be asked to practice achieving and holding their breath during the expiration phase.

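### The aspirin trial's primary contrast, PMBF on aspirin versus placebo, has no detectable difference in the power section; the only PMBF figure is scaled to an on/off-AAT-replacement SD

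*Combined protocol and SAP*

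**What the plan says.** Section 2.e.i sets the endpoint of the aspirin RCT: "Primary endpoint: pulmonary microvascular blood flow". Section 3.a sets the contrast and the test: "The primary analysis will use paired t-tests to compare pulmonary microvascular blood flow on aspirin compared to placebo". Under section 2.f the two measurements compared are those at Visits 2 and 3, each at the end of a treatment period.

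Section 3.b describes the power calculation differently: "Power was estimated for a paired t-test to compare an individual's pulmonary microvascular blood flow before and after the intervention". For 15 subjects, 80% power and alpha 0.05 it reports "a minimally significant difference of 48.4 mL blood/min*100mL lung", and explains this as "1.6 times the SD of the difference in pulmonary microvascular blood flow [PMBF] for those on replacement and not". It also gives 0.30 log units, or 1.2 SD, for CD31+ EMPs. It adds that the source was cross-sectional, calls the estimate conservative for that reason, and rates power as moderate for PMBF.

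Section 2.e.ii makes CD31+ EMPs the primary endpoint of the withdrawal study and lists PMBF among its secondary endpoints. On scan timing, section 5, item 11 says: "The MRI exam will be performed at visits 2-4". Table 1 agrees and shows no PMBF measurement at screening.

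**The concern.** The contrast that is tested and the contrast that is powered do not match. Section 3.a tests aspirin against placebo within a person. Section 3.b describes a before/after comparison and uses an SD that belongs to AAT replacement. No SD, expected effect or power figure for PMBF on aspirin versus placebo appears anywhere else in the protocol.

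What is at stake is interpretation. The figure of 48.4 and the rating of moderate power are the only benchmarks a reader has for the aspirin trial's sensitivity. A null aspirin result would be read against them although they were not derived for that comparison.

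**Working it through.** **1. Which contrast does the 48.4 belong to?** There are two readings of the intervention in section 3.b.

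- *Aspirin* (the usage in section 2.f). No pre-treatment PMBF is measured: the first MRI is at Visit 2, already the end of treatment 1. The SD is still one for AAT replacement.
- *AAT withdrawal* (the reading that fits the SD label). A before/after comparison exists, with Visits 2 and 3 before and Visit 4 after. PMBF on versus off AAT is then a secondary endpoint of the withdrawal study.

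On neither reading is the figure for end of aspirin versus end of placebo.

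**2. Inputs (section 3.b).** n = 15 pairs; power 80%; alpha 0.05. Sidedness is not stated, so two-sided is assumed. The implied PMBF SD is 48.4/1.6 = 30.25 and the implied CD31+ EMP SD is 0.30/1.2 = 0.25.

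**3. Attempt to reproduce the plan's figure.** The detectable standardised difference d solves

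P(|T| > t(0.975; 14 df)) = 0.80, with T noncentral t on 14 df and noncentrality d × √15.

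- Result: d = 0.778 (normal approximation 0.723; one-sided 0.675).
- The printed 1.6 SD is not reproduced. Raising power to 95% gives only 1.002.
- At 1.6 SD a 15-pair test has 99.99% power, and at 1.2 SD 99.1%.
- With the same n, alpha and power, a paired test gives one multiple for both endpoints, so 1.2 and 1.6 cannot both come from it.
- A two-independent-group t-test with 15 people in all gives 1.57 SD for a 7/8 split and 1.60 for a 6/9 split. That would fit a cross-sectional on/off comparison, but the splits are an assumption and are not in the protocol.

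**4. Detectable aspirin-placebo difference.** It equals 0.778 × SD of the within-person difference. The protocol does not give that SD, so two assumptions are shown.

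(a) The label is taken literally and 30.25 is the SD of a paired difference: 0.778 × 30.25 = 23.5 mL/min per 100 mL.

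(b) 30.25 is a between-person SD, as the cross-sectional source suggests, equal at both visits, with within-person correlation r. Then SD of the difference = 30.25 × √(2(1 − r)):

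| r (assumed) | SD of difference | Detectable difference |
|---|---|---|
| 0 | 42.8 | 33.3 |
| 0.3 | 35.8 | 27.8 |
| 0.5 | 30.25 | 23.5 |
| 0.7 | 23.4 | 18.2 |
| 0.9 | 13.5 | 10.5 |

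**5. The CD31+ EMP figure under the same test.** Taking the implied SD literally, 0.778 × 0.25 = 0.19 log units, against the printed 0.30.

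**The case against.** The best defence is that the analysis itself is clear from sections 2.e.i and 3.a, and that the before/after phrase is loose wording. Borrowing an SD from the same disease and the same measure is ordinary practice for a small crossover. Section 3.b discloses the origin of the SD in the same sentence and calls the result conservative. The 48.4 is a detectable difference rather than an assumed effect, so only its SD needs a source. No sample size, visit or test would change.

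Much of this stands. The primary test is not in doubt, and a borrowed SD can be acceptable. What is missing is any statement that the AAT figure stands in for aspirin versus placebo, and any reason why it should. The one caveat given concerns cross-sectional versus within-person data and does not address the change of treatment. Loose wording also cannot explain the SD label, which is explicit.

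A reader might draw three stronger conclusions that the protocol does not support:

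- *The trial is underpowered.* Every value in the table lies below 48.4, and no expected aspirin effect is given, so power for aspirin cannot be computed.
- *The gap between 48.4 and the recomputed values measures the wrong contrast.* Most of it is the separate multiplier error, which alone contributes 1.6/0.778 = 2.06. At r = 0.5 the SD does not change at all, and at r = 0.3 the SD of the difference exceeds 30.25.
- *No before/after PMBF comparison exists in this study.* That is true only if the intervention is aspirin.

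**Conclusion.** The point holds as a mismatch within the plan: the primary contrast of the randomised trial has no stated detectable difference, and the only PMBF figure belongs to a secondary contrast of the withdrawal study. This conclusion needs no assumed numbers.

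The size can be given only conditionally. For 15 pairs the detectable difference is 0.778 SD of the within-person difference: 23.5 mL/min per 100 mL on the literal label, or between 33.3 and 10.5 for r from 0 to 0.9. These values rest on two-sided 0.05, on the implied SD of 30.25 and, for the range, on equal variances and an assumed r. The consequence is for how the result is read, not for the conduct of the trial.

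**What to change.** In section 3.b:

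1. Name the powered contrast as PMBF at the end of aspirin versus the end of placebo (Visits 2 and 3), and state that the test is two-sided if that is intended.
2. Say explicitly that the on/off-replacement SD is borrowed, whether it is a between-person SD or the SD of a paired difference, and why it is a reasonable stand-in.
3. Restate the detectable difference as 0.778 SD of the within-person difference, with 23.5 or the range over r above, according to what the SD is.
4. Report the on/off-AAT figures separately under the withdrawal study, with CD31+ EMPs as primary and PMBF as secondary. Recompute both with the 0.778 multiple (about 0.19 log units for CD31+ EMPs if 0.25 is the SD of the paired difference); do not carry over 0.30 and 48.4.

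The cost is one rewritten paragraph and one recalculation, with no change to enrolment, visits or tests. The drawback is that, unless a repeat-scan SD can be found, the aspirin figure has to be shown as a range.
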